## Study Endpoints

A high-contrast, black and white image showing a series of horizontal bars of varying lengths and positions, suggesting a digital or abstract data visualization. The bars are composed of black pixels on a white background. There are three main horizontal groups of bars. The top group has a long bar on the right and a shorter bar on the left. The middle group has a very long bar on the right and a shorter bar on the left. The bottom group has a long bar on the right and a shorter bar on the left. The bars are composed of black pixels on a white background.

## Specific Aim 2:

### **Primary and secondary endpoints for Aim 2:**

The primary study endpoint will be intrahepatic lipid content.

11. **What is the primary purpose of the following statement?**

1. **What is the primary purpose of the study?** (check all that apply)

## Methods:

**Intrahepatic lipid accumulation:** We will perform proton MR spectroscopy (1H-MRS) of the right and left hepatic lobe to determine intrahepatic lipids (IHL) using a 3Tesla MRI device (Siemens Trio, Siemens Medical Systems, Erlangen, Germany) as we have previously described. Advantages of higher magnetic field strength are an increase in signal-to-noise ratio resulting in improved spatial resolution and increased chemical shift dispersion, potentially improving assessment of other fat resonances. MRI sequences are also performed for assessment of other fat depots and [REDACTED] analysis within the same session.

Adipokines: Adiponectin (total, high molecular weight, medium HMW forms) will be measured by enzyme-linked immunosorbent assay [REDACTED]. Leptin will be measured by ELISA [REDACTED]. Coefficients of variation (CVs) are less than 10% for all assays.

Inflammatory markers: hsCRP will be measured by latex particle-enhanced immunoturbidmetric assay on a Hitachi 911 analyzer [REDACTED]. IL-6 will be measured using an immunoassay [REDACTED]. TNF-alpha receptor subtypes (both 1 and 2) will be measured by ELISA [REDACTED]. CVs are less than 10% for all assays.

Liver function tests: A standard liver function test panel consisting of ALT, AST, GGT, alkaline phosphatase, total bilirubin, direct bilirubin, indirect bilirubin, ferritin and albumin will be measured using a standard clinical platform.

Lipids and Lipoproteins: A fasting lipid profile, including total cholesterol, LDL, HDL and triglycerides, will be determined. OxPL levels will be performed in conjunction with the laboratory of [REDACTED] has pioneered the use of OxPL in CVD. OxPL markers will be measured in three ways; 1. OxPL/ApoB: amount of oxidized phosphorylcholine on LDL, 2. ApoB IC: measurement of immune complexes of IgG or IgM to ApoB, and 3. Malondialdehyde (MDA:LDL) autoantibodies. Comprehensive lipid profiling will be performed in conjunction with [REDACTED]

[REDACTED]. Ion mobility analysis is a validated method using gas-phase differential electrophoretic macromolecular mobility to distinguish lipid subfractions.

[figure not shown]

The NAFLD fibrosis score: This score predicts the probability of fibrosis in patients with NAFLD using a score that uses the patient's age, body mass index, blood glucose levels, aminotransferase levels, platelet count, and albumin. A high NAFLD fibrosis score of >0.676 is associated with a probability of advanced fibrosis (F3-F4) of 82 percent (sensitivity 43 percent, specificity 96 percent), and a score of <-1.455 is associated with a negative predictive value of 88 percent (sensitivity 77 percent, specificity 71 percent) based on prior studies.

[REDACTED] Elastography [REDACTED] is a rapid non invasive technique that measures liver stiffness by transmission of mild amplitude and low frequency (50Hz) through the intercostal space using a vibrator at the skin surface. The vibration induces a shear wave velocity through

the hepatic tissue, which is directly related to tissue stiffness and is expressed in kilopascals (kPa). Transient Elastography is an inexpensive, reproducible, painless, rapid <10 minutes and easy to perform tool. It has been proven in many studies to correlate well with degree or severity of fibrosis and or cirrhosis.

For studies involving treatment or diagnosis, provide information about standard of care at Partners (e.g., BWH, MGH) and indicate how the study procedures differ from standard care. Provide information on available alternative treatments, procedures, or methods of diagnosis.

Treatment of NAFLD is extremely limited at this point in time. Patients are recommended to make lifestyle adjustments with a goal of weight loss, such as maintaining a healthy diet and

exercise program, which would not be affected by this study. This is the only standard of care at this time. Various other therapies for NAFLD have been tested, however, lack of robust evidence for improvement of NAFLD has limited their incorporation into clinical care. Currently NAFLD patients are monitored in the Fatty Liver Clinic and are referred for liver transplant if they develop decompensated cirrhosis, however, we will not be recruiting this end stage population. Therefore, the GH therapy in this trial would be one additional therapeutic option that could be offered to patients with NAFLD who inherently have extremely limited treatment options.

Describe how risks to subjects are minimized, for example, by using procedures which are consistent with sound research design and which do not unnecessarily expose subjects to risk or by using procedures already being performed on the subject for diagnostic or treatment purposes.

A number of procedures will be instituted to protect against potential risk involved in this protocol. The potential effects of growth hormone on a fetus are not known and therefore precautions against administration to pregnant patients will be instituted. All patients will have pregnancy tests on admission prior to receiving radiation or study medication. Subjects will also have serial pregnancy tests – one at every study visit – and study participation will be discontinued if a subject becomes pregnant. Due to COVID-19, subjects will be allowed to perform a pregnancy test at home for any remote visit and on the day of any in-person visit in order to minimize potential exposures. The subject will share this result with the study team for documentation.

A portion of this research study involves exposure to radiation from up to six CT scans (three single slice scans per session with sessions at baseline and six months) and up to five DXA scans (3 bone sites plus body composition studied at baseline and only body composition studied at the 6 month visit).

Subjects completing Aim 2 (prospective) of the study will be exposed to a total of 0.60 mSV of radiation from completing each of the studies listed above twice (once at baseline and once at 6 months). This amount of radiation is about three months of radiation from natural background sources. Any subject who completes Aim 1 and subsequently completes Aim 2 will not have additional radiation exposure beyond what a subject completing only Aim 2 would receive (a total of 0.60 mSv).

GH will be administered to subjects in Specific Aim 2 only. Side effects of GH administration could include mild swelling or arthralgias, which occur in a minority of patients and resolve after the first few days of therapy in the vast majority of patients. In those study subjects in whom such side effects do not resolve, we will reduce the dose. Additionally, any study subject with a fasting glucose in the diabetic range at the 3-month visit will be discontinued from the study, and

fasting glucose will be retested 3 months later. We will ask permission from all study subjects to communicate with a healthcare provider about any abnormal clinically relevant test results.

A physician will be available at all times during the study by pager to answer any questions a patient might have. The physician will arrange to immediately see every patient with a concern. All efforts will be made to protect the confidentiality rights of the study subjects who will be referred to by code numbers only. Confidentiality of the patients will always be of paramount importance to study investigators. No data on patients will be shared with persons other than those directly involved in the study, except at the documented request of the patient. Samples that are sent to laboratories outside of [REDACTED] will be labeled with a non-identifying numeric code.

All adverse events will be reported to the IRB in a timely manner according to the guidelines provided by Partner's Human Subjects Research Committee.

Describe explicitly the methods for ensuring the safety of subjects. Provide objective criteria for removing a subject from the study, for example, objective criteria for worsening disease/lack of improvement and/or unacceptable adverse events. The inclusion of objective drop criteria is especially important in studies designed with placebo control groups.

Safety assessments for subjects in Aim 2:

1. IGF-I levels:
  - a. Must have IGF-I within or below the lowest-3 quartiles for age and gender
  - b. Measurements at screening, baseline, 1 month, 2 months, 3 months and 6 months
  - c. Dose decrease for IGF-I levels above the upper limit of normal
2. Glucose: Fasting glucose at screen as well as 1, 3 and 6 month visits.
3. Pregnancy testing at all visits
4. HbA1c: screening, 3 month and 6 months
5. Liver function tests: screening, 1 month, 3 month and 6 months

Subjects will be discontinued from Aim 2 of the study if they develop

1. Diabetes mellitus: fasting glucose  $\geq 126$  mg/dl or HbA1c  $\geq 6.5\%$
2. Positive pregnancy test
3. Severe / intolerable side effects of GH
4. Development of malignancy
5. Initiation of the following medications: OCPs and pioglitazone
6. Elevated AST/ALT  $>10 \times$  the upper limit of normal OR if there is a  $>25\%$  increase from baseline, whichever is greater.

## FORESEEABLE RISKS AND DISCOMFORTS

Provide a brief description of any foreseeable risks and discomforts to subjects. Include those related to drugs/devices/procedures being studied and/or administered/Performed solely for research purposes. In addition, include psychosocial risks, and risks related to privacy and confidentiality. When applicable, describe risks to a developing fetus or nursing infant.

Because IGF-I levels, an integrated measure of GH secretion, will be raised to within the normal range appropriate for age and gender and not above, we expect the risks of GH administration to subjects in Specific Aim 2 to be minimal. Our experience in administering GH, at the doses proposed in this protocol, to healthy men and women with low GH levels (not related to hypopituitarism), we should expect minimal if any side effects. Such side effects could include headaches, mild swelling or arthralgias, which occur in a minority of patients and resolve after the first few days of therapy in the vast majority of patients. In those study subjects in whom such side effects do not resolve, we will reduce the dose. If mild side effects occur and do not resolve, the study drug will be discontinued until the side effects resolve. After resolution of side effects, the study drug will be restarted at the lower dose that did not cause any side effects.

The net effect of GH on insulin resistance appears to be neutral, despite two opposing effects of GH on insulin resistance – direct negative effects and indirect positive effects mediated through dramatic changes in body composition. Most studies have shown an acute worsening of insulin resistance followed by chronic improvement or lack of change. The most similar paradigm available in the literature is a study by Johannsson *et al.* in which normal obese men were randomized to receive GH or placebo for 9 months. Acutely insulin sensitivity, as measured by the gold standard hyperinsulinemic, euglycemic clamp deteriorated slightly, and this was followed with an improvement compared with baseline at 9 months.

Subjects will undergo low dose CTs of the thigh and abdomen at one visit for subjects in Aim 1 and at two visits for subjects in Aim 2. [REDACTED]

[REDACTED]. The combined radiation from all procedures for the entire study for subjects in Aim 2 is approximately 0.60 mSv – this amount of radiation is equal to approximately 3 months of natural background radiation [REDACTED]. [REDACTED]. Blood drawing may result in bruising or infection at the venipuncture site.

MRS and MRI will be performed using FDA approved devices and pulse sequences. There are no known foreseeable risks associated with exposure to MRI, provided there are no metallic implants (i.e., vascular clamps or pacemakers). All potential subjects will be screened for the presence of such prior to the exam. Some subjects do report some claustrophobia during the scan. If a patient expresses any discomfort during the scan, the procedure will be aborted and not repeated without his/her full consent. Subjects will be required to lie in a magnet for about 1 hr. The 3.0T MR device is FDA-approved for clinical use. No serious or lasting side effects associated with the use of MRI have been reported. Rarely, subjects report sensations such as vertigo and a metallic taste when exposed to magnetic fields. Minor theoretical hazards arise from rapid gradient switching and RF transmission. All parameters used for conventional and spectroscopic imaging fall within FDA limits for specific absorption rates (SAR) of RF

transmission and rapid gradient switching (dB/dt). Experiments properly conducted in compliance with FDA, OSHA and standard safety practices of the [REDACTED] pose no significant risk to research subjects. MR examinations will be performed by a Radiological Technologist certified by the Commonwealth of Massachusetts. Any adverse events will be reported immediately to the [REDACTED].

[REDACTED]

[REDACTED]

[REDACTED]

[REDACTED]

[REDACTED]

[REDACTED]

[REDACTED]

[REDACTED]

[REDACTED]

Growth Hormone and Intrahepatic Lipid Content in Patients with Nonalcoholic Fatty Liver Disease

NCT# 02217345

Version Date: 2/17/2022

Statistical Analysis Plan

A. Study endpoints

Primary Endpoint: Change in intrahepatic lipid accumulation over 6 months in the GH vs placebo group.

Secondary Endpoints: Change in the following endpoints over 6 months in the GH vs placebo group.

1. Liver function tests
2. Adipokines: leptin and adiponectin
3. Inflammatory markers: hsCRP, IL-6 and TNF alpha receptors
4. Measures of insulin resistance
5. Abdominal fat compartments
6. NAFLD Fibrosis Score
7. ELF Score
8. Liver stiffness by Fibroscan
9. Liver inflammation and fibrosis by Liver *MultiScan*

B. Experimental approach:

A total of approximately 65 otherwise healthy subjects with NAFLD and relatively low IGF-1 levels will be enrolled after a screening visit at which study eligibility will be determined with a history, physical exam, blood work, IGF-1 level and hemoglobin A1C. Eligible subjects will be randomized to receive GH or placebo. GH reserve will be characterized at baseline. Subjects will be studied for 6 months. We plan to enroll up to 65 individuals and will attempt to replace subjects who have dropped out of the study to ensure 50 completers at 6 months.

C. Statistical power and Analysis

Power Calculation: A total of approximately 65 patients will enter this two-treatment parallel-design study with enrollment of up to 50 completers. With 40 completers, the probability is increased to 90 percent that the study will detect a treatment difference in percent intrahepatic lipid content at a two-sided 0.05 significance level, if the true difference between treatment with GH and placebo is 6.5%. With 50 completers, the probability is 90 percent that the study will detect a treatment difference in percent intrahepatic lipid content at a two-sided 0.05 significance level, if the true difference between treatment with GH and placebo is 5.7%. This is based on the assumption that the standard deviation of the response variable is 6.1% as observed in Wong *et. al.*¹ Studies available for power calculations include all comers with NAFLD, and our study population is restricted to those without diabetes who are more likely to have a lower severity of disease. Additionally, there is recognized variability in the natural history of NAFLD, particularly in early stage disease. For these reasons, we will attempt to replace subjects who have dropped out of the study to ensure 50 completers at 6 months.

Data Analysis Plan: We will pool data from men and women using a random slopes model; we will consider a model where each study subject has a random slope and intercept. The primary analysis is a pooled analysis of treatment effect across gender with weights equaling the frequency of men and women in the sample. A secondary analysis will test for the significance of the treatment-gender interaction on the rate of change of intrahepatic liver fat and all other endpoints. For all analyses, an intent-to-treat analysis will be performed.

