### **Aim 2:**

## Aim 2, n=65 subjects (50 completers), approximately 50% women

The baseline visit will occur within 12 weeks of the screening visit. The following assessments will be made at the baseline visit:

1. Interview to determine whether any changes in medical history since the screening visit has occurred.
2. BMI will be calculated and waist-hip-ratio measured.
3. In the fasting state, a blood sample will be obtained to determine glucose, insulin,

GH, gonadal steroid levels and other hormone levels (including ghrelin, testosterone, free testosterone, estradiol and SHBG), adipokines, inflammatory markers, and ELF score liver function tests.

4. A 2-hour 75-gm oral glucose tolerance test for glucose and insulin (Aim 1 Only) and a 2-hour GHRH-arginine GH stimulation test will be performed
5. MRI: 1H-MRS of the right and left hepatic lobe will be performed to quantify hepatic lipid content and other fat depots. [REDACTED] sequences will also be performed for noninvasive analysis of hepatic inflammation and fibrosis.
6. A single slice CT of each of the following areas will be performed (for a total of three single slice CT scans): the abdomen at the level of L4, the liver, and the mid-thigh to quantify abdominal (visceral and subcutaneous) fat, liver fat, thigh fat and thigh muscle area.
7. Dual energy x-ray absorptiometry (DXA) scan will be performed to determine body composition of the whole body and assessment of bone density.
8. The Paffenbarger Physical Activity questionnaire, NHANES Dietary Screener Questionnaire, and the SF-36 health survey questionnaire will be administered.
9. Resting energy expenditure (REE) using indirect calorimetry, bioelectrical impedance analysis (BIA) to estimate body composition and total body water assessment will be performed.

A nutritionist will perform an assessment of resting energy expenditure. The subject will be lying on a bed in a private room for 30 minutes. Then, a clear plastic canopy will be fitted over the subject's head and upper chest to collect the air he or she exhales for 30 additional minutes. The entire procedure takes approximately 60 minutes to complete.

The bioelectrical impedance analysis uses a small electric current to measure the body's electrical resistance. The data can be used to provide an accurate measure of body composition and total body water.

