**[REDACTED] Subjects completing Aim 2 proceed to randomization and follow up visits as noted below.**

*Randomization for Aim 2:* Study subjects in Aim 2 only will be randomized to receive GH injections or to the placebo (control) group. Randomization will be stratified by sex.

*Starting Doses for Aim 2:* GH or placebo will be initiated via a subcutaneous injection in Aim 2 subjects only at a dose of 0.2 mg in men and 0.3 mg daily in women in patients randomized to the GH arm.

*One, 2 and 3-month follow-up visits for Aim 2 Only:*

1. Interim medical history and side effects to study drug will be assessed.

2. Physical exam will be performed.
3. An IGF-1 level will be measured, and dose adjustments made to target the upper quartile of the normal, age-appropriate IGF-1 range.
4. Pregnancy tests will be performed at both visits in premenopausal women.
5. Fasting glucose will be measured at the 1 and 3-month visit and HbA1c will be performed at the 3-month visit as safety labs. Both fasting glucose and HbA1c are performed at study completion at 6 months.
6. Liver function tests will be performed at screening, 1 month, 3 months and 6 months as safety labs.

**Remote Visits:** Subjects who do not live locally will have the option to perform three follow up visits (1 month, 2 month, and 3 month visits) remotely. These will be performed with remote labs (via Quest Diagnostics Locations) and medical history via phone call with a study physician or nurse practitioner. For these remote visits, the study doctor or nurse will speak to the subject over the phone to obtain a medical history, and at those visits a physical exam would not be performed. The remote visit will be converted to an in-person visit if there is any concern based on updated history or symptoms at the discretion of the visit medical provider. For these remote visits, the study team will FedEx study medication to the subject in a manner approved by the research pharmacy as needed for resupply. The subject would bring back unused study medication and empty vials to the study team at the next in person visit to maintain standard study drug accountability logs. Additionally, for off-site visits, a serum pregnancy test will be performed in all women of childbearing age and status.

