**Six-month follow-up visit for Aim 2 Only:** The 6-month visit will be performed during a +/- 2 week interval around the indicated return time to allow for potential scheduling conflicts. At this visit, the identical procedures described under Baseline Study Visit will be repeated with the exception the DXA for bone density and GHRH-arginine stimulation test, which are only completed at the baseline visit. Six month laboratory assessment includes a fasting blood sample obtained to determine glucose, insulin, GH, IGF-1, CBC, gonadal steroid levels and other hormone levels (including ghrelin, testosterone, free testosterone, estradiol and SHBG), adipokines, inflammatory markers, ELF score, lipids, triglycerides, and liver function tests. Subjects will be asked to collect an at-home stool sample using a provided kit and bring it with them to their final study visit. Then, study drug will be discontinued. This is the study end.

**Note regarding pregnancy tests:** Due to COVID-19, subjects will be allowed to perform a pregnancy test at home for any remote visit and on the day of any in-person visit in order to minimize potential exposures. The subject will share this result with the study team for documentation.

**1 Month Post-Study Follow Up Call:** A study provider will attempt to contact subjects four weeks after study completion to document subject status at that time, which will be approximately one month after study drug discontinuation.

[REDACTED]

[REDACTED]

[REDACTED]

[REDACTED]

The image consists of a series of horizontal bars, primarily black, set against a white background. The bars are of varying lengths and are positioned at different heights. Some bars are longer and centered, while others are shorter and located towards the top or bottom. The overall effect is abstract, resembling a digital signal or a stylized bar chart.

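### Liver fat is scanned only at baseline and month 6, so the planned random intercept-and-slope model cannot separate random slope from residual; one baseline-adjusted two-visit model should replace it

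*SAP*

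**What the plan says.** SAP section A defines the primary endpoint as the 6-month change in intrahepatic lipid, GH against placebo. In SAP section C, the Data Analysis Plan pools men and women in a random slopes model and continues: "we will consider a model where each study subject has a random slope and intercept". The treatment effect is averaged over the sex frequencies, a treatment-by-sex interaction is a secondary test, and every analysis is intent-to-treat. The SAP gives no list of fixed effects, no covariance structure and no time scale.

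The measurement schedule is in the protocol:

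- Baseline visit, item 5: "1H-MRS of the right and left hepatic lobe will be performed to quantify hepatic lipid content and other fat depots".
- Six-month visit: "the identical procedures described under Baseline Study Visit will be repeated". The listed exceptions do not include MRS. On timing: "The 6-month visit will be performed during a +/- 2 week interval around the indicated return time".
- Month 1, 2 and 3 visits: history, examination, IGF-1, pregnancy tests and safety labs, with no imaging. For subjects who live far away they may be remote: "These will be performed with remote labs (via Quest Diagnostics Locations) and medical history via phone call".
- Methods: "We will perform proton MR spectroscopy (1H-MRS) of the right and left hepatic lobe to determine intrahepatic lipids". The visible text does not say how the two lobe values become one.

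**The concern.** A random slope is a subject's own rate of change, and the residual is the scatter around that subject's line. With two points per subject the line passes through both, so nothing is left to separate slope variation from scatter. The primary model as described may fail to fit, and the SAP gives no covariance restriction that would rescue it.

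A second gap matters more for the result. Without a list of fixed effects, a reader cannot tell whether the arms are given a common baseline mean. That choice decides whether the baseline scan is used to gain precision. At stake are some precision and a primary analysis that can be reproduced from the SAP, not the validity of the comparison.

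**Working it through.** **Inputs.** From SAP section C: differences of 5.7 (50 completers) and 6.5 (40 completers), SD 6.1, two-sided 0.05, power 90%. Assumed, because the documents do not give them: 1:1 allocation; 6.1 as the SD of change (the SAP says only that it is the SD of the response variable); and the baseline to month-6 correlation r, taken as 0.5, 0.7 and 0.9.

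**1. The plan's own power.** For an unadjusted two-sample t-test the noncentrality is (difference/SD) × √(n/2), with n per arm.

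- 50 completers: (5.7/6.1) × √12.5 = 3.30, 48 df, power 89.9%.
- 40 completers: (6.5/6.1) × √10 = 3.37, 38 df, power 90.7%.

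Both stated figures reproduce.

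**2. Counting parameters.** Let a be the intercept variance, b the slope variance, c their covariance and e the residual variance, with time 0 and 6 months. One value per visit gives three observable quantities:

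- Var(baseline) = a + e
- Cov(baseline, month 6) = a + 6c
- Var(month 6) = a + 12c + 36b + e

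That is four unknowns in three equations; the Jacobian has rank 3 of 4. Raising e by δ, lowering a by δ, raising c by δ/6 and lowering b by δ/18 leaves all three unchanged. Example with an assumed visit variance of 100: a change SD of 6.1 gives a covariance of 100 − 6.1²/2 = 81.4. Residual variances of 0, 5, 10, 15 and 18 then all give the same matrix (100, 81.4, 100), each with a valid random-effects matrix.

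**3. Ways to identify it.**

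- Setting c = 0 leaves three parameters and rank 3. It also forces the month-6 variance to be at least the baseline variance, since the difference is then 36b.
- Entering the two lobes as separate responses gives rank 4, but treats lobe differences as the residual.
- Using actual dates within the ±2-week window gives rank 4 only formally: with 50 subjects and a true residual variance of 10, its standard error is about 40.

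The SAP specifies none of these.

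**4. Effect on fitting.** In 20 simulated trials, one package's default optimiser converged in none and another optimiser in all 20. In one simulated data set of 50 completers, the estimated effect was the same in every fit and equalled the difference in mean change. The standard error was 1.89 in the non-converged fit and 1.46 in the converged one; the simple change-score standard error was also 1.46.

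**5. What the unlisted fixed effects decide.** With complete data, fitting a treatment effect at time 0 reproduces the change-score comparison exactly. Omitting it (a common baseline mean) gives essentially ANCOVA. With equal visit SDs, the effective SD after adjustment is 6.1 × √((1 + r)/2). Allowing for the sex and sex-by-treatment terms leaves 45 df.

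| r | effective SD | power at 5.7, 25 per arm | difference detectable at 90% |
|---|---|---|---|
| change score | 6.10 | 89.9% | 5.71 |
| 0.5 | 5.28 | 96.2% | 4.95 |
| 0.7 | 5.62 | 93.9% | 5.27 |
| 0.9 | 5.95 | 91.3% | 5.57 |

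Simulated ANCOVA, which also carries chance baseline imbalance, gives 95.7%, 93.5% and 90.6%.

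**6. When adjustment does not help.** With k the ratio of month-6 to baseline SD, the variance ratio of adjusted to change score is k²(1 − r²)/(1 + k² − 2rk). At r = 0.8 and k = 1.25 it is 0.5625/0.5625 = 1. Simulation there gives a ratio of 1.02 and power of about 89.2%, a loss of about 0.7 points.

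**7. Missing scans.** With 65 randomised and 15 month-6 scans missing at random, simulated power at 5.7 is 91.4%, 90.6% and 89.7% with a time-0 treatment effect, and 96.1%, 94.0% and 91.3% with a common baseline (r = 0.5, 0.7, 0.9). The latter figures are slightly flattering, because the unadjusted standard error is about 2% too small. Bias is at most 0.02 throughout.

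**The case against.** The strongest reply is that only a nuisance split is unidentified. A random intercept and slope with free covariance implies an unstructured 2×2 covariance, which is what the fix uses, and a converged fit gives the right estimate and standard error. This stands, and it limits the severity.

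The endpoint wording, the SAP's reference to rate of change, and the power calculation all favour the change-score reading, which keeps the stated 90%. That also stands. The remaining case is that the reading has to be inferred and usually gives up precision.

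Three stronger readings are tempting but not supported:

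- A reader might infer that the primary analysis is biased or cannot be carried out. It is neither.
- A reader might take the verb in the quoted clause to make the model optional. The words before it commit to a random slopes model, so the clause can equally be a description of that model.
- A reader might infer an inflated type I error. If someone ran both versions and reported whichever was significant, the false-positive rate would be 7.4%, 6.8% and 5.9% at r = 0.5, 0.7 and 0.9. That is a worst case for a model chosen after seeing results, and nothing in the SAP indicates such a practice.

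On the lobes, Methods refers to an earlier description and parts of the endpoint text are redacted. One can say only that no combining rule appears in the visible text.

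**Conclusion.** The concern holds in a limited form and should be fixed. For liver fat entered as one value per visit with a free intercept-slope covariance, the variance components are not identified. This is exact and needs no assumed figures. The consequences are possible non-convergence and optimiser-dependent standard errors, not a biased treatment effect.

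The gain from naming a baseline-adjusted model is roughly 1 to 6 points of power at 5.7 with 50 completers. It depends on the assumed r, equal visit SDs, 1:1 allocation and 6.1 being the SD of change; at r = 0.9 it is small. If 6.1 is instead a single-visit SD, change-score against adjusted power is 78% and 92% at r = 0.3, 90% and 96% at r = 0.5, and 98.7% and 99.5% at r = 0.7.

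The point covers endpoints measured only at baseline and month 6. It does not extend to the liver function tests: "Liver function tests will be performed at screening, 1 month, 3 months and 6 months as safety labs".

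**What to change.** Replace the model sentence in the Data Analysis Plan with one primary model for intrahepatic lipid, fixed before unblinding:

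- two visits, with visit as a category and an unstructured 2×2 covariance;
- a common baseline mean across arms, which randomisation justifies;
- sex and treatment-by-visit-by-sex terms, with the month-6 effect averaged over the sex frequencies and the interaction tested as already planned (the protocol states: "Randomization will be stratified by sex");
- REML with a small-sample adjustment such as Kenward-Roger;
- all randomised subjects with at least one scan, under a stated missing-at-random assumption, in keeping with the intent-to-treat statement.

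State the rule that gives one liver-fat value per visit from the two lobes. Keep ANCOVA of month-6 on baseline lipid as a sensitivity analysis only, since it drops subjects without a month-6 scan. Use the same model for secondary endpoints measured only at these two visits.

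The cost is SAP wording and a few degrees of freedom (about 45 instead of 48 with 50 completers). Power falls by at most about 0.7 points, when the regression slope of month-6 on baseline lipid is near 1. Scans and sample size are unchanged.
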